14.3 Appendix 3: Eastern Cooperative Oncology Group (ECOG) performance status

Score	Performance status
0	Fully active, able to carry on all pre-disease performance without restriction.
1	Restricted in physically strenuous activity but ambulatory and able to carry out work of a light or sedentary nature, e.g. light housework, office work.
2	Ambulatory and capable of all self-care but unable to carry out any work activities. Up and about more than 50% of waking hours.
3	Capable of only limited self-care, confined to bed or chair more than 50% of waking hours.
4	Completely disabled. Cannot carry on any self-care. Totally confined to bed or chair.
5	Dead

14.4 Appendix 4: Adaptive Basket Trial for Combination Immune-therapy in Patients with Advanced Solid and Lymphoma

1 Introduction

This document outlines the adaptive design framework to be used for a single-arm Phase II study for the investigation combination immune-therapy across multiple cancer subtypes.

Seven pre-specified tumor cohorts, (also referred to as “groups”) are planned for the analysis:

Small-cell lung cancer (SCLC)	Gastroesophageal
Soft tissue sarcoma (STS)	Prostate
Ovarian	Advanced NET
Diffuse large B-cell lymphoma (DLBCL)	

The primary endpoint in each group is clinical benefit rate (CBR) assessed at 24 weeks. All patients will receive the experimental treatment.

The trial incorporates analyses based on a hierarchical model that allows for the possibility that the effect profile for the population of tumor types may be homogeneous or heterogeneous. There may be ‘clusters’ or subsets of tumor types – some in which the treatment is effective, and others not. The analysis borrows information, in a limited sense, from the tumor types that demonstrate similar CBR effects based on the trial data. The clustering used to characterize the distribution of tumor via a Dirichlet process prior (Escobar & West, 1995; Neal, 2000) is solely based on the observed CBRs. As described in Berry et al. [Berry, 2013], borrowing via a hierarchical model is a type of shrinkage estimation; it provides a formal mechanism by which extreme observations are shrunk toward the mean.

Prospectively, the model is developed by evaluating its performance from simulated trials. Hence, the false-positive rate can be controlled and power assessed. The advantages to borrowing are 1) increased precision of CBR estimates and 2) better decisions regarding CBRs.

2 Primary Analysis

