6.4 Example Trials

6.4.1 Overview

In this section, we present an example of the trial to illustrate the adaptive process.

The trial is described graphically in a series of plots. Each plot describes the current data at the time of the interim. The plots include the following features:

- Light gray bars represent the number of subjects enrolled.
- Dark gray bars represent the number of subjects with CBR data
- Bars may be outlined blue, yellow, red, or green. Blue indicates a group may continue to enroll; yellow indicates that enrollment has been paused for the group; red indicates a group has permanently stopped for futility; and green indicates a group has declared success.
- Vertical dashed lines are provided at 10 and 24 subjects.
- Text columns to the right of the plot display the following summary statistics for each group:
 - Pr(>Ctrl): The probability that the CBR exceeds that group's corresponding historical control based on the hierarchical model
 - Data: The observed number of events/the number of subjects with CBR data available
 - Obs. CBR: The observed CBR

- Est. CBR: The model-estimated CBR
- Red/green diamonds at n=10 indicate whether a group has met its expansion threshold (no go/go). Once a group has expanded beyond n=10, this gate remains green.
- The historical control for each group is displayed on the left side in orange.

In the simulations, interims occur every 13 weeks. Hence, a large number of interims may occur per trial. For this example, we show results for a small number of select interims in order to highlight the features of the adaptive design.

6.4.2 Example Trial 1

6.4.2.1 Example Trial 1, Interim 1

The trial begins enrolling subjects across all groups. The first interim analysis (Figure 12) occurs at 31 weeks from the first subject enrolled. Decisions (for futility or sample size expansion) can only be made for groups that have at least 5 subjects with CBR data available. No groups have CBR data available from at least 5 subjects, and therefore, no groups can stop for futility or enroll beyond 10 subjects until the next interim analysis. Groups 2 and 3 have already enrolled 10 subjects and therefore pause enrollment. This enrollment pause will be re-evaluated at the next interim analysis.

[figure not shown]

Figure 12 – Example trial 1, interim 1

6.4.2.2 Example Trial 1, Interim 2

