8.2 Mean Squared Error

The mean squared error (MSE) is a measure of the average value of $(\text{estimate} - \text{truth})^2$. It incorporates both the bias and variance associated with the estimate. The MSE values for the borrowing analysis are consistently lower than that of independent analyses.

Group	All Great	All Null	Half	3 Great	3 Null	Mixed
1	0.002/0.007	0.001/0.004	0.002/0.007	0.001/0.003	0.002/0.007	0.001/0.005
2	0.009/0.018	0.008/0.016	0.009/0.017	0.015/0.019	0.009/0.017	0.013/0.019
3	0.008/0.016	0.010/0.019	0.011/0.017	0.010/0.019	0.010/0.017	0.010/0.020
4	0.009/0.017	0.007/0.016	0.008/0.016	0.008/0.016	0.011/0.018	0.009/0.017
5	0.008/0.017	0.005/0.012	0.011/0.017	0.013/0.017	0.006/0.012	0.011/0.017
6	0.009/0.017	0.009/0.019	0.009/0.019	0.009/0.019	0.011/0.019	0.009/0.019
7	0.009/0.018	0.005/0.014	0.012/0.020	0.005/0.014	0.011/0.019	0.008/0.017

Table 18 – MSE (borrowing/independent analyses)

[figure not shown]

Figure 20 – MSE (borrowing versus independent analyses)

9 Comparison of Design Approaches: Planned Design with or without Early Futility prior to Sample Size Expansion

Simulated trial data has been applied to two designs:

1. The planned design as described in this report but with early futility prior to sample size expansion removed
2. The planned design as described in this report

The former approach describes the design (including sample size expansion and post-expansion futility stopping) but without early futility stopping prior to sample size expansion. If early futility stopping were permitted, a fraction of the trials (this varies based on the scenario and group) will halt enrollment earlier than it otherwise would have and prohibit those groups from ultimately meeting success. For groups that would otherwise have met success, the early futility leads to a missed success and reduction in power. While for groups that did not ultimately meet success, the early futility stopping provides a savings in patients and resources. Inherent in the futility stopping is a trade-off between power reduction and subject savings. The goal is to minimize any potential reduction in power while allowing the design to reduce its required sample size required to determine success in each group.

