The final analysis will occur when both accrual and follow-up are complete for all groups. If, at the completion of the trial, there is at least 80% probability that the response rate in a group exceeds the historical rate, then the group will be considered a success. Formally:

$$\Pr(\pi_g > R_g) > 0.80.$$

In addition of above mentioned Bayesian analyses with all solid tumor types combined and separately for each hematological tumor type, the CBR estimate will be provided with its 95% exact CI. For tumor types (within the solid tumors) that have ten (10) or more patients, separate summaries will be performed by the tumor type and will also be displayed graphically. In the event that there are fewer than 4 patients for a hematological tumor type, only listing will be provided for that tumor type. In addition to summary by tumor types, separate summaries will also be provided by prior line of therapy and number of treatment cycles received.

CBR estimate with its 95% exact CI will also be provided for CBR by end of study using full analysis set. Additionally, for tumor cohort Prostate cancer an association of response(CBR) with PSA(prostate specific antigen) will be explored by summarizing the response at different level of PSA stratified by quartiles at baseline and 24 week.Similar analysis will also be repeated for ovarian cancer with Cancer Antigen-125 (CA-125).

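### SAP 2.5.2 names no model-based CBR estimate for reporting: the only one specified is x/n with an exact CI, which by the plan's own Table 18 has about twice the mean squared error of the model estimate

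*SAP*

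**What the plan says.** SAP 2.5.2 defines the primary analysis by Pr(π_g > R_g), where π_g is the cohort's CBR and R_g its historical rate. The thresholds are below 0.20 for early futility, above 0.70 for expansion, below 0.60 for post-expansion futility, and above 0.80 for final success. A cohort succeeds if "there is at least 80% probability that the response rate in a group exceeds the historical rate".

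The reporting sentence follows under Final Analysis. It opens "In addition of above mentioned Bayesian analyses" and says that, for all solid tumours combined and "separately for each hematological tumor type, the CBR estimate will be provided with its 95% exact CI". Solid tumour types get their own summary only with ten or more patients. SAP 5.4.2 gives the interval as Clopper-Pearson. Neither section names a posterior mean, posterior median or credible interval for CBR.

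For model details the SAP points to Protocol Appendix 4. Section 1 there says: "The advantages to borrowing are 1) increased precision of CBR estimates and 2) better decisions regarding CBRs". Section 8.2 says: "The MSE values for the borrowing analysis are consistently lower than that of independent analyses". The plot legend in Section 6.4.1 includes "Est. CBR: The model-estimated CBR". Section 7 describes the posterior of θ_g (the log-odds difference from R_g) as the quantity behind the design's decisions and does not list it as a reported estimate.

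**The concern.** The design gives better estimation as its first reason for borrowing, yet the analysis plan commits to an estimate that does not borrow. The success call and the CBR printed beside it then come from two different analyses.

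This is a signal-seeking trial meant to show whether efficacy warrants further study, so the CBR of a successful cohort is likely to be carried into later planning. As specified, that number is the less precise of two already available. It also takes no account of the fact that a cohort's size (stopped early, 10 or 24) depends on its own outcomes.

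**Working it through.** **1. The plan's own figure.** Table 18 prints borrowing/independent MSE for 7 groups and 6 scenarios. Two of its columns are headed 3 Great and 3 Null; they are read here as the 2 Great and 2 Null scenarios of Table 2. Ratio = independent MSE ÷ borrowing MSE. For group 2, All Great: 0.018 ÷ 0.009 = 2.0.

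| Group | All Great | All Null | Half | 2 Great | 2 Null | Mixed |
|---|---|---|---|---|---|---|
| 1 SCLC | 3.50 | 4.00 | 3.50 | 3.00 | 3.50 | 5.00 |
| 2 | 2.00 | 2.00 | 1.89 | 1.27 | 1.89 | 1.46 |
| 3 | 2.00 | 1.90 | 1.55 | 1.90 | 1.70 | 2.00 |
| 4 | 1.89 | 2.29 | 2.00 | 2.00 | 1.64 | 1.89 |
| 5 | 2.13 | 2.40 | 1.55 | 1.31 | 2.00 | 1.55 |
| 6 | 1.89 | 2.11 | 2.11 | 2.11 | 1.73 | 2.11 |
| 7 | 2.00 | 2.80 | 1.67 | 2.80 | 1.73 | 2.13 |

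- All 42 cells: minimum 1.27, median 2.0, maximum 5.0. Ratio of sums: 0.653 ÷ 0.343 = 1.90.
- Without SCLC: 1.27 to 2.8, median 1.95.
- On the percentage-point scale: √2.0 = 1.41 at the median; without SCLC, √1.27 = 1.13 to √2.8 = 1.67.
- The 5.0 is a rounding-sensitive cell printed 0.001/0.005. The unrounded ratio could lie between 0.0045 ÷ 0.0015 = 3 and 0.0055 ÷ 0.0005 = 11.

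**2. Is the independent column the observed proportion?** Appendix 4 Section 8 says both columns come from the same adaptive design and differ only in the final analysis, but does not spell out the estimator. A rough check for group 2, All Null is R(1−R) ÷ mean n = 0.435 × 0.565 ÷ 14.7 (Table 9) = 0.0167, against 0.016 printed.

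**3. Re-simulation.** Inputs from Appendix 4:
- Dirichlet parameter 2, μ ~ N(0, 1.82), τ² ~ IG(3, 0.5)
- Table 1 accrual as a Poisson process, 24-week follow-up, no dropout
- interims every 13 weeks, the 0.20/0.70/0.60/0.80 rules, at most 24 patients per cohort

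Appendix 4 does not say whether 1.82 is a variance or an SD, so both were run (2,500 trials per scenario as variance, 1,200 to 1,500 as SD).

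| Check | Plan | Re-simulation |
|---|---|---|
| Mean trial size, All Great | 150.6 | 150 to 151 |
| Mean trial size, All Null | 94.3 | 94 to 95 |
| MSE group 2, All Great (model/raw) | 0.009/0.018 | 0.008/0.016 to 0.017 |
| MSE, all 42 cells | Table 18 | model within 0.0016, raw within 0.0024 |
| Table 3 success probabilities within 2 points | – | 34 of 42 (SD), 29 of 42 (variance) |

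The independent column therefore behaves as x/n. The simulated median MSE ratio was 2.0 to 2.1 under either reading of 1.82.

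**4. Bias (estimate minus truth, percentage points).** The success rows exclude the Mixed scenario.

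| Cohorts | x/n | Model |
|---|---|---|
| Truly effective, declared a success | +3 to +6 | +1 to +2 |
| Null, declared a success | +8 to +16 (average about +14) | +6 to +13 (average about +11 to +12) |
| All cohorts, x/n only | −1 to −4 | – |

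For two effective cohorts among mostly ineffective ones (2 Great), the model estimate was about 5 points low on average because of shrinkage.

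**The case against.** The exact-CI line is expressly an addition to the Bayesian analyses, and the SAP defers details to an appendix that displays a model-estimated CBR. An observed proportion with an exact interval does not depend on the priors and is easy to check. The gain from borrowing is smallest (1.27 and 1.31) for the two effective cohorts in 2 Great, which is the isolated signal a basket trial looks for. Selection on success inflates the model estimate too. The patient sets may also differ: Appendix 4 Section 3 keeps up to 6 exploratory patients per cohort out of the primary analysis, while the SAP full analysis set states no such exclusion.

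Most of this stands, and it limits the point to an unspecified output. It does not remove the point: the SAP still commits to no posterior estimate or interval, and Table 18 favours the model in every cell.

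Some stronger readings are tempting but not supported:
- **That the SAP rules out a model estimate, or uses the model only for the final call.** The sentence says in addition, and the model also drives interim futility and expansion.
- **That x/n is biased upward in general.** Over all cohorts it is slightly low because of futility stopping; the inflation is conditional on success.
- **That the exact interval is shown to be worse than a credible interval in falsely successful cohorts.** Coverage of the two was not compared there, and selection affects both.
- **That the pooled solid-tumour CBR is judged against an unstable null.** The SAP compares each cohort with its own historical rate and gives the pooled line no reference.

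**Conclusion.** The point holds as a reporting gap that is cheap to close. The SAP specifies only the less precise of two available CBR estimates, contrary to the design's stated reason for borrowing. The size is about twice the mean squared error, or about 1.4 times the error in percentage points; reading it as twice the error in points would be wrong. In truly effective successful cohorts the model removes more than half of the inflation. In null cohorts wrongly declared a success it removes little, so it does not cure selection bias.

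The MSE ratios are the plan's own figures. The bias figures rest on the Appendix 4 assumptions (accrual, no dropout, the six effect scenarios) and on both estimates using the same patients, at most 24 per cohort.

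**What to change.** In SAP 2.5.2, specify for every cohort, including solid cohorts below ten patients, the posterior mean (or median; choose one) and 95% credible interval of π_g and of π_g − R_g from the final MCMC run. Make this the estimate that accompanies the success decision. Keep x/n with its exact CI beside it, and say which patients each line includes.

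Add two sentences of interpretation. First, both estimates are subject to selection in cohorts declared a success, and the model corrects this only in part, least of all in null cohorts. Second, the model pulls isolated effective cohorts towards the others, so x/n must stay visible.

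The cost is SAP wording and one table from draws that the final analysis already produces. The SAP history records an update after database lock; if this output is added after results are known, it should be labelled as such.

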7.1.4 Treatment period

A treatment cycle is defined as 21 days for the purposes of scheduling procedures and evaluations. Please refer to [Table 7-1](#) for details of the timing of required assessments and [Section 7.1](#) for visit windows.

Patients will receive study treatment for a maximum of 2 years, or until disease progression (assessed by investigator per RECIST 1.1 and the Revised Response Criteria for Malignant Lymphoma criteria (Cheson et al 2007) for lymphoma), unacceptable toxicity, death or discontinuation from study treatment for any other reason (e.g., withdrawal of consent, start of a new anti-neoplastic therapy or at the discretion of the investigator or patient), otherwise known as End of Treatment.

Clinical experience indicates that objective responses to immunotherapy follows delayed kinetics of weeks or months, and can be preceded by initial apparent radiological progression or appearance of new lesions or some enlarging lesions while other target lesions are regressing (“mixed response”) ([Wolchock 2009](#)). Therefore, patients with disease progression, may remain on treatment, if the Investigator considers it to be in the patient’s best interest, and after documented discussion with the Novartis Medical Monitor.

These considerations should be balanced by clinical judgment as to whether the patient is clinically deteriorating and unlikely to receive any benefit from continued treatment.

Patients with an unconfirmed progressive disease who show signs of clinical deterioration or toxicity will enter the 150-day safety follow-up period. Such deterioration will be assessed to have occurred after a clinical event that, in the investigator's opinion, is attributable to disease progression, is unlikely to reverse with continued study treatment and therefore indicates that the patient is not benefiting from study treatment and cannot be managed by the addition of supportive care.

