1.1 Study design

1.1.1 Description of study design

This is a phase II, open-label study to determine the efficacy and safety of treatment with the combination of PDR001+LAG525 across multiple tumor types that are relapsed and/or refractory to available standard of care therapies. The study will be conducted in 35-210 patients with select solid tumors or lymphoma as outlined in [Table 1-1 Tumor Groups](#) Seven pre-specified tumor cohort (groups) planned for the analysis are as follows:

Table 1-1 Tumor Groups

Group	Malignancy
1	Small-cell lung cancer
2	Gastric/esophageal adenocarcinoma
3	Castration resistant prostate adenocarcinoma (CRPC)
4	Soft tissue sarcoma
5	Ovarian adenocarcinoma
6	Advanced well-differentiated neuroendocrine tumors
7	Diffuse large B cell lymphoma (DLBCL)

Tumor cohorts may be excluded or added during the course of the study in the case of early futility or success based upon an interim analysis or at the discretion of Novartis based on emerging pre-clinical or clinical data .

Patients will receive study treatment for a maximum of 2 years, or until disease progression, unacceptable toxicity, death or discontinuation from study treatment for any other reason (e.g., withdrawal of consent, start of a new anti-neoplastic therapy or at the discretion of the investigator or patient). All patients who discontinue from study treatment due to disease

progression must have their progression clearly documented. All disease assessments will be performed locally by the investigator.

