2.2.3 Subgroup of interest

Some specific efficacy analyses will also be repeated in the following subgroup as appropriate. .

1. Tumor cohorts.
2. Prior line of therapy(1,2, and ≥ 3)
3. Number of treatment cycles(less than 3 cycles, ≥ 3 cycles, Less than 5, ≥ 5 cycles)

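### The CBR summary by number of treatment cycles received will show a large difference even for an inactive drug; the week-24 PSA and CA-125 quartile tables cover a small subset selected by outcome

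*SAP*

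**What the plan says.** SAP 2.5.2 adds descriptive CBR tables to the Bayesian primary analysis: "separate summaries will also be provided by prior line of therapy and number of treatment cycles received". SAP 2.2.3 lists the cuts as "Number of treatment cycles(less than 3 cycles, ≥ 3 cycles, Less than 5, ≥ 5 cycles". For prostate cancer, SAP 2.5.2 also plans to explore an association between CBR and PSA by "summarizing the response at different level of PSA stratified by quartiles at baseline and 24 week", and a similar "analysis will also be repeated for ovarian cancer with Cancer Antigen-125 (CA-125".

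Other sections link these groupings to the outcome:

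- Dosing (SAP 1.1.1): "Patients will receive study treatment for a maximum of 2 years, or until disease progression". Protocol 7.1.4 allows an exception: "patients with disease progression, may remain on treatment, if the Investigator considers it to be" in the patient's interest.
- Cycle length (Protocol 7.1.4): "A treatment cycle is defined as 21 days".
- Scans (Protocol 4.1 and 7.2.1.1): first at week 12, then weeks 18 and 24. PSA and CA-125 follow the same schedule (Protocol Table 7-1).
- Scoring (SAP 2.5.3): a patient without a valid radiological assessment is a non-responder. Under SAP 2.5.2, progression given as the reason for stopping treatment also counts as progressive disease.

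No landmark, time-dependent method or caution accompanies these tables.

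**The concern.** A subgroup for an efficacy endpoint should be fixed before the endpoint can influence it. Prior line of therapy and baseline marker level meet that test. Cycles received does not: progression both stops the count and turns the patient into a CBR failure, so sorting by cycles partly sorts by outcome.

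A week-24 marker value has a related fault. Having one depends largely on still being on study at week 24, and most such patients already have clinical benefit.

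This is a signal-seeking study, and CBR rising with the number of cycles is easily read as a dose or exposure effect. The same pattern would appear if the combination did nothing.

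**Working it through.** **Inputs.** Median PFS by tumor type and exponential PFS (Protocol Appendix 4, section 6.1.2, Table 1; medians repeated in SAP Table 2-1). Cycles of 21 days, so dose *k* is due at week 3(*k* − 1): dose 3 at week 6 and dose 5 at week 12.

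**Reproducing the plan's null.** S(t) = 0.5^(t/median). With 24 weeks taken as 6 months, S(6) is 0.5^(6/3) = 25.0% (ovarian), 0.5^(6/4) = 35.4% (prostate), 0.5^(6/5) = 43.5% (gastro-esophageal) and 0.5^(6/1.5) = 6.25% (SCLC). These match the table. Taking 24 weeks as 5.54 months would give 27.8% for ovarian, so the plan uses the 6-month convention. I keep it: week 6 = 1.5 months, week 12 = 3, week 18 = 4.5.

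**CBR by cycles, no drug effect.** Assume that progression is the only reason for stopping and ends dosing at once. A patient reaches dose 5 only if progression-free at week 12, so week-24 CBR is S(6)/S(3) with 5 or more cycles and 0 with fewer. At the 3-cycle cut it is S(6)/S(1.5) versus 0.

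| Tumor type | Overall | <5 | ≥5 | <3 | ≥3 |
|---|---|---|---|---|---|
| SCLC | 6.25% | 0% | 0.0625/0.25 = 25% | 0% | 0.0625/0.50 = 12.5% |
| Ovarian | 25% | 0% | 0.25/0.50 = 50% | 0% | 0.25/0.707 = 35.4% |
| Prostate | 35.4% | 0% | 0.354/0.595 = 59% | 0% | 0.354/0.771 = 45.9% |
| Gastro-esophageal | 43.5% | 0% | 0.435/0.660 = 66% | – | – |
| All seven, weighted by planned accrual | 31.1% | 0% | 58.6% | 0% | 43.4% |

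Under SAP 2.5.2, best response of SD or better within 24 weeks counts. In this model everyone with 5 or more cycles was progression-free at the week-12 scan, so the 5-cycle cut gives 0% versus 100%, with 53.0% overall.

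**Robustness (simulation, 400,000 patients per type).** If progression is found only at scans, and the week-12 result is known before dose 5, the weighted contrast is 0% versus 58.5%. With 20% dropout for other reasons (my assumption; the plan's simulations assume none), the upper group is still 52-53%. With scan-only detection the <3-cycle row is empty unless there is other dropout. With 10-20% dropout it holds 2.6-5.4% of patients, all non-responders.

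**Week-24 marker.** If values come only from patients progression-free at week 24, CBR is 100% in every quartile under either definition. If patients progressing between weeks 18 and 24 are also measured, CBR under the SAP definition is still 100% throughout. Under the week-24 definition it averages S(6)/S(4.5):

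- Prostate: 0.354/0.459 = 77.1%, against a null of 35.4%.
- Ovarian: 0.250/0.354 = 70.7%, against a null of 25%.

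Across quartiles this is flat if the marker is unrelated to PFS. At an assumed correlation of 0.6 it runs from 86% to 68% (prostate) and 80% to 62% (ovarian), lowest to highest quartile. Of 24 patients, 24 × 0.354 = 8.5 to 24 × 0.459 = 11.0 (prostate) and 24 × 0.25 = 6.0 to 24 × 0.354 = 8.5 (ovarian) would have a value, or between 1.5 and 2.75 per quartile.

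**The case against.** **The exact 0% is a modelling result.** This stands. Dose 4 is due at week 9. A patient with SD at the week-12 scan who then stops for toxicity has fewer than 5 cycles and still counts as a success under SAP 2.5.2. Dose delays shift cycles (Protocol 6.3.1), so a delayed patient can have SD at week 12 with fewer than 5 doses. Treatment beyond progression puts some failures in the upper group, as does giving dose 5 before the week-12 scan is read. All this narrows the gap, but the cycle count still depends on not progressing.

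**Early stoppers are not failures by rule.** This also stands. A reader might infer that fewer than 3 cycles means no scan and hence failure. Protocol 7.2.1 requires prompt assessment on clinical suspicion of progression, Protocol 4.1 allows extra assessments, and Protocol Appendix 1 (14.1.17) accepts SD from one assessment more than 6 weeks after start. The row may also hold very few patients.

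**The marker tables need not show a gradient.** This stands too. A reader might infer that low week-24 PSA or CA-125 will appear to go with benefit whatever the drug does. Under the SAP definition CBR is the same in every quartile in this model. A slope needs the week-24 definition, values taken at or after progression, and a marker that tracks progression. What remains is inflated CBR in a small selected subset.

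**The tables are descriptive.** SAP 2.1 plans no testing outside the primary variable, and whole-cohort CBR is reported as well. That limits the harm. It does not make a table informative when an inactive drug would produce the same pattern. Protocol Appendix 1 (14.1.23 and 14.1.24) itself warns of selection bias in responder-only analyses, and the reasoning carries over.

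**Conclusion.** The concern about cycle count holds. Followed as written, SAP 2.2.3 and 2.5.2 will give a large CBR difference by cycles received with no drug effect. At the 5-cycle cut it is about 0% versus 50% (ovarian), 59% (prostate) and 66% (gastro-esophageal) at week 24, with the upper group approaching 100% under the best-response definition. These sizes rest on exponential PFS at the plan's historical medians, 24 weeks taken as 6 months, and progression as the only reason for stopping. The observed contrast will be softer.

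The week-24 marker tables have a lesser fault: a small subset selected by remaining on study, with CBR of about 71-100% against null rates of 25-35%, and a gradient that is possible but not assured.

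A reader might go further and infer that the trial's success decision is biased. The documents do not support that: neither split enters the futility, expansion or final success rules. The tables should still be changed, because they are planned outputs of a signal-seeking trial and cannot separate an active drug from an inactive one.

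**What to change.** 1. Delete number of treatment cycles as an efficacy subgroup in SAP 2.2.3 and 2.5.2. Keep prior line of therapy.
2. For PSA and CA-125, keep baseline quartiles and drop the week-24 quartiles.
3. If exposure is still of interest, use a week-12 landmark. Among patients progression-free at week 12, report CR/PR/SD status at week 24 by cycles received up to week 12. Use the protocol's week-24 definition, because under best response by week 24 SD at the landmark scan already counts as benefit.

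Under the null, with 20% of doses missed at random (assumed), the landmark gives equal CBR in the higher- and lower-dose groups: 59.5% and 59.5% (prostate), 49.6% and 49.7% (ovarian), 66.1% and 65.9% (gastro-esophageal).

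**Cost:** fewer descriptive tables and a logged SAP change (the document history already records changes after database lock). The landmark table will offer little contrast in small cohorts, since most patients progression-free at week 12 will have had 4 or 5 cycles.
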